### 8.2 Interim Analysis

No interim analysis is planned for this study. A Data Safety Monitoring Board (DSMB) will be utilized for this study to monitor subject safety.

### 8.3 Handling of Missing Data

In general, data analysis will be performed on the basis of all available data.

For missing values of primary endpoints, multiple imputations will be performed and sensitivity analysis will be conducted for primary endpoints. The multiple imputation will be performed with SAS PROC MI, using the regression method for monotone missing pattern, with the covariates treatment arm, clinician, anesthetic agent, and subject ASA status as the independent variables. A total of 5 imputed data sets will be generated and analysis of primary endpoints will be performed on each imputed data set. PROC MIANALYZE will be used to summarize the results from imputed data sets.

Clinician recorded end tidal target values are considered missing, when a recorded target is not available for a setting adjustment resulting in a significant change in end tidal measurements. If the change in end tidal measurement results in more than 5% v/v O2, 0.9% v/v DES, 0.31% v/v SEV, or 0.15% v/v ISO from the previous end tidal measurement over a period of 2 minutes, then the recorded target data is considered missing. This portion of the data is not used for the purpose of the analysis with the clinician recorded target values.

**Study Title:** Multi-site Anesthesia randomized controlled Study of End tidal control (Et Control) compared to conventional anesthesia Results (MASTER-Anesthesia Trial)  
**Study No:** 123.07-2015-GE5-0002

GE Healthcare

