
Hypothesis/Analysis
	
The hypotheses for the primary endpoints are: H0: <math>\mu_{et} - \mu_{con} < -5\%</math> vs H1: <math>\mu_{et} - \mu_{con} \geq -5\%</math> for both EtAA and EtO2, where <math>\mu_{et}</math> is the average percent duration of Et Control with EtAA and EtO2 maintained within the acceptable range, and <math>\mu_{con}</math> is the average percent duration of control device with EtAA and EtO2 maintained within the acceptable range.
 
Data collected will be presented using summary tables, data listings, and graphs. Study endpoints and parameters will be summarized using descriptive statistics. Descriptive statistics for continuous variables will include mean, standard deviation, median, Q1 and Q3, minimum, maximum, and sample size. For comparison between arms (or against null values), categorical variables will be tested using appropriate contingency table analyses, and continuous variables will be tested using Student's t- test or non-parametric methods. P-values will be presented to 3 decimal places, and p-values less than 0.001 will be presented as '<0.001.' No imputation will be performed for missing data.
 
The analysis of the primary endpoints will consist of:
 
 
◆ the analysis on ITT population based on the algorithm determined end-tidal concentration (scenario 1) and clinician's recorded set target end-tidal concentration (scenario 2); AND
 
◆ patients of different ASA status.
 
	

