## 6. PROCEDURES FOR RESEARCH STUDY

### 6.1 Randomization and Enrollment

Subjects will be randomized at a ratio of 1:1 to either the "Investigational Et Control Arm" or the "Control Arm." Stratified randomization will be used based on Investigator, subject's pre-existing hypertension status, and subject's ASA status. Randomization sequences will be

**Study Title:** Multi-site Anesthesia randomized controlled Study of End tidal control (Et Control) compared to conventional anesthesia Results (MASTER-Anesthesia Trial)  
**Study No:** 123.07-2015-GES-0002

GE Healthcare

assigned through the IVRS/IWRS system. Subjects will be considered enrolled after providing written informed consent.

The following devices will be employed for each arm of the study:

- ♦ **Investigational Et Control Arm:** legally marketed Aisys CS anesthesia machine with investigational Et Control option
- ♦ **Control Arm:** legally marketed Aisys CS anesthesia machine without the investigational Et Control option

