### 8.1.2 Statistical Methods Overview

Data collected in this study will be presented using summary tables, data listings and graphs. Study endpoints and parameters will be summarized using descriptive statistics.

The descriptive statistics for continuous variables will include mean, standard deviation, median, Q1 and Q3, minimum, maximum, and sample size. Categorical variables will be described with counts, percentages, and sample size.

For comparison (between arms or against null values), categorical variables will be tested using appropriate contingency table analyses (exact or chi-square approximations), and continuous variables will be tested using Student's t-test or non-parametric methods, depending on variable distribution. P-values will be presented to three decimal places and p-values less than .001 will be presented as '<.001.'

**Study Title:** Multi-site Anesthesia randomized controlled Study of End tidal control (Et Control) compared to conventional anesthesia Results (MASTER-Anesthesia Trial)  
**Study No:** 123.07-2015-GES-0002

GE Healthcare

Subjects using different anesthetic agents will be pooled for analysis per the arm they are randomized. Separate analysis may be performed by anesthetic agent when pooling data across anesthetic agents is not appropriate.

No imputation will be performed for missing data unless specified otherwise.

A data extraction algorithm is used to identify periods of end tidal concentration measurement stability following setting changes (i.e. Steady States) during a case, as well as to measure response times, settling times, and overshoot amounts from these steady states in order to compare across arms. The extraction algorithm is not part of the statistical analysis, but provides the above-mentioned endpoints. (See Appendix 2 – Extraction algorithm for more information on the extraction algorithm.)

There will be two scenarios in defining a step change and steady state when performing the data extraction: 1) *using the data extraction algorithm to determine the desired end-tidal concentrations of anesthetic agent and oxygen for both arms* (See Appendix 2 – Extraction algorithm for more information on the extraction algorithm); 2) *using the clinicians recorded end tidal target values of anesthetic agent and oxygen for the Control arm, and the set target value for the Et Control arm.*

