#### 8.1.3 Analysis of Primary Endpoints

Separate analysis of primary endpoints will be performed on the basis of the extracted data for the following scenarios: 1) *using the algorithm to determine the desired end-tidal concentrations of anesthetic agent and oxygen for both arms; and 2) using the clinicians*

**Study Title:** Multi-site Anesthesia randomized controlled Study of End tidal control (Et Control) compared to conventional anesthesia Results (MASTER-Anesthesia Trial)  
**Study No:** 123.07-2015-GES-0002

GE Healthcare

*recorded target values of anesthetic agent and oxygen for the Control Arm and using the set target values for the Et Control Arm.*

Analysis of primary endpoints will be based on ITT population, evaluable population, and per protocol population. The conclusion will be based on the ITT population.

For EtAA and EtO2 respectively, percent duration with EtAA and EtO2 maintained within the acceptable range will be calculated for each steady state. And the per subject weighted average of the percent duration will be calculated for each subject using the duration of each steady state as the weight.

Using t-test, comparison of the weighted average percent duration between the Et Control and control device will be performed by calculating the difference and its 95% 2-sided confidence interval between the two arms. Non-inferiority will be concluded if the lower limit of the 95% confidence interval is  $\geq -5\%$  for both EtAA and EtO2, and superiority will be concluded if the lower limit of the 95% confidence interval is  $> 0$  for EtAA and the lower limit of the 95% confidence interval is  $\geq -5\%$  for EtO2.

The primary analysis for the primary endpoints consists of the analysis on ITT population based on the algorithm determined end-tidal concentration (scenario 1) and clinician's recorded set target end-tidal concentration (scenario 2). This primary analysis will also be performed for patients of different ASA status.

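### The synopsis rules out the imputation that Section 8.3 requires, the plan does not say which ITT result decides, and five imputations leave avoidable seed noise in the confidence limit

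*Combined protocol and SAP*

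**What the plan says.** Four places in the combined protocol and SAP bear on missing primary endpoints.

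- Synopsis, Hypothesis/Analysis row: "No imputation will be performed for missing data". No exception follows, and the same row sets out the ITT primary analysis.
- Section 8.1.2: "No imputation will be performed for missing data unless specified otherwise".
- Section 8.3, general rule: "In general, data analysis will be performed on the basis of all available data". For the primary endpoints it then says: "For missing values of primary endpoints, multiple imputations will be performed and sensitivity analysis will be conducted for primary endpoints". The method is regression imputation in SAS PROC MI "with the covariates treatment arm, clinician, anesthetic agent, and subject ASA status as the independent variables", and "A total of 5 imputed data sets will be generated". No seed is given, and the sensitivity analysis is not described.
- Section 8.1.3: "The conclusion will be based on the ITT population". Section 8.1.2.1 defines ITT as every randomized subject. The test is an unadjusted t-test with a 95% interval.

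On stratification, Section 6.1 says "Stratified randomization will be used based on Investigator" and adds pre-existing hypertension and ASA status. Hypertension is not among the imputation covariates, which also list clinician where the stratum is Investigator. Table 8-1 inflates the sample size for 15% dropout.

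**The concern.** The study passes if the lower 95% limit is at or above −5 for both EtAA and EtO2 (Sections 8.1.3 and 8.4). The deciding population is all randomized subjects, but Section 8.1.3 does not say how a subject without an endpoint enters the t-test. Section 8.3 puts imputation and sensitivity analysis in one sentence. It can be read as making the imputed result primary, or as making imputation the sensitivity analysis on top of available data. A third reader who stops at the synopsis would not impute at all. The pass/fail number is therefore not uniquely defined.

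If the imputed result decides, two analysts with different seeds will report different limits. The stated regression model also assumes that data are missing at random, and no less favourable assumption is named. Section 11.1 lists termination criteria tied to Et Control's own performance. Data collected before withdrawal are kept (Section 11.3). If such a case left no usable steady state, however, its missingness could be related to poor control, and a missing-at-random model would then favour Et Control.

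**Working it through.** **1. The plan's sample size (Section 8.1.1, Table 8-1).** The inputs are one-sided alpha 0.025, power 0.95 per endpoint and a margin of 5.

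- EtAA: expected difference 90 − 87 = +3, SD 16. Normal approximation: n = 2 × 16² × (1.960 + 1.645)² / (5 + 3)² ≈ 104 per arm. The t-test calculation gives 105. Then 105 / 0.85 = 123.5, so 124 per arm and 248 in total, as stated.
- EtO2: difference +8, SD 19 gives 57 per arm. Then 57 / 0.85 = 67.1, so 68 per arm and 136 in total, as stated.

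The plan thus budgets for about 0.15 × 248 = 37 subjects without an endpoint and is powered on about 105 observed per arm.

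**2. Where the expected EtAA limit lies.** SE = 16 × √(2/105) = 2.21. The lower limit is about 3 − 1.97 × 2.21 = −1.35, which is 3.65 points above −5.

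**3. Efficiency with m imputations.** The documents give no fraction of missing information, so I assume 0.15 (range 0.05 to 0.30). Relative efficiency is 1 / (1 + FMI/m). With m = 5 it is 1 / 1.03 = 97.1% (99.0% at FMI 0.05, 94.3% at 0.30). The SE is inflated by √1.03 − 1 = 1.5%. Lost precision is not the problem.

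**4. Seed noise.** The SD of the point estimate across seeds is roughly SE × √(FMI/m) = 2.21 × √(0.15/5) = 0.38 points. The limit varies more, because its estimated variance also depends on the seed. I simulated 124 per arm with 19 missing per arm at random, SD 16 and a true difference of +3, using normal-model imputation, Rubin's rules and Barnard-Rubin degrees of freedom:

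| Imputations | SD of lower limit across seeds (points) |
|---|---|
| 5 | 0.51 |
| 20 | 0.23 |
| 50 | 0.14 |
| 100 | 0.10 |

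A run on a single simulated data set gave 0.46, 0.21, 0.14 and 0.09. With 5 imputations, two SDs are about ±1 point, a fifth of the margin. The noise falls with less missing data: with 5 imputations it is 0.36 at 12 missing per arm and 0.23 at 6 per arm.

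**5. Effect on the conclusion.** If the limit free of seed noise lies 0.5 points from a boundary, a seed SD of 0.5 gives the opposite conclusion about one time in six. Over whole simulated trials with 5 imputations, two seeds disagreed on EtAA non-inferiority in about 3% of trials at a true difference of +3. At the feasibility difference of +7 (94 − 87) they disagreed in 0.05% or fewer.

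**6. Imputed against available-data limit.** Under missing at random, with no covariates beyond arm, the imputed limit averages about 0.1 points lower with 5 imputations and about 0.01 lower with 100.

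**The case against.** A reader might infer that the plan contradicts itself throughout. It does not. Section 8.1.2 sets a default with room for exceptions, and 8.3 states the exception for the primary endpoints. The available-data sentence in 8.3 is qualified as a general rule. Only the synopsis sentence lacks the qualifier.

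The choice of rule also changes little under missing at random (step 6), and with 5 imputations the shift is slightly conservative. The 15% is a sample-size allowance, not a forecast of missing endpoints. The endpoint comes from breath-by-breath machine logs during one anaesthetic, so actual missingness may be lower. Cases shorter than 45 minutes leave the evaluable set but can still contribute to ITT. At the planned effect the limit sits well away from −5.

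A reader might also infer that omitting hypertension biases the result. The analysis is an unadjusted t-test, so the imputation model omits no term of the analysis model, and nothing in the documents links hypertension to end-tidal stability.

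Finally, whether the imputed result should decide is open. Letting available data decide would match the complete-case sample size and keep seed noise out of the pass/fail result.

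All of this stands, and it limits the size of the point. It does not remove the synopsis conflict, the unnamed deciding result or the undescribed sensitivity analysis. The small difference in step 6 says nothing about data missing not at random.

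**Conclusion.** The concern holds in a limited form. The synopsis conflicts with Section 8.3, and Sections 8.1.3 and 8.3 leave the deciding ITT result undefined. If the imputed result decides, the stated 5 imputations add a seed-to-seed SD of about 0.5 points to the lower limit, against about 0.1 with 100. That size rests on 15% missing per arm, SD 16 and data missing at random; with fewer missing it is smaller. It matters only when the limit falls near −5, or near 0 for EtAA superiority. The documents do not support a stronger reading, namely that the conclusion is generally at the mercy of the seed or that the estimate is biased. The missing hypertension term is a minor tidiness point. The absence of any named analysis beyond missing at random is a real gap, though its effect cannot be computed from the documents.

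**What to change.** 1. In the synopsis, add an exception pointing to Section 8.3.
2. In Section 8.1.3 or 8.3, state in advance which ITT result decides, imputed or available-data, and make the other supportive. Either choice is defensible; leaving it open is not.
3. Replace 5 imputations by about 100 and record a fixed seed. If the available-data result decides, this only steadies the supportive analysis.
4. Name the sensitivity analysis: subtract an increasing delta from the imputed Et Control values until non-inferiority is lost, and report that delta.
5. As a minor addition, put pre-existing hypertension in the imputation model and align clinician with the stratum Investigator.

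The cost is SAP wording, minutes of computing and one extra table. Sample size, enrolment and conduct do not change.

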## 8.4 Pass/Fail Criteria of the Study

Successfully meeting the non-inferiority test for both EtAA and EtO2 in the primary endpoints fulfills the pass criteria of the study.

## 9. DEVIATIONS

### 9.1 Management of Protocol Deviations

Deviations to the protocol may occur when necessary to protect the life or physical well-being of a subject. Except in an emergency, prior approval by the Sponsor is required for changes in, or planned deviations from this protocol. If these changes affect the scientific integrity or the safety and welfare of the subject, prior IRB approval is also required. Planned Protocol Deviation documentation must be filed in the Site Study Regulatory Binder.

There are two types of unplanned protocol deviations, critical deviations and non-critical deviations. All deviations must be documented and reported, the criticality of the deviation will determine the reporting path.

**Critical Deviations:** Deviations that significantly affect the safety, efficacy, integrity or conduct of the study. These deviations must be reported to the Sponsor no later than 5 working days from awareness of occurrence and reported to the IRB per the deviation reporting policy.

If an Investigator uses the investigational device without obtaining informed consent, the Investigator shall consider this a critical deviation and report the event to the Sponsor and the IRB within 5 working days of the occurrence.

The Sponsor shall inform the FDA within five (5) working days of the use of the investigational device without obtaining informed consent.

The critical deviation(s) will be reported via the electronic case report form. A copy will be submitted to the study Sponsor via fax, e-mail, or courier and the original will remain on site where it will be reviewed by the study monitor.

**Non-Critical Deviations:** Protocol deviations that do not significantly affect the safety, efficacy, integrity or conduct of the trial. These deviations must be documented on the Electronic Case Report Form Protocol Deviation page and will be reviewed by the study monitor.

**Study Title:** Multi-site Anesthesia randomized controlled Study of End tidal control (Et Control) compared to conventional anesthesia Results (MASTER-Anesthesia Trial)  
**Study No:** 123.07-2015-GE5-0002

GE Healthcare

## 10. COMPLAINT HANDLING AND ADVERSE EVENT REPORTING

### 10.1 Foreseeable Adverse Events and Device Effects

Being in this study involves some foreseeable risks. The following are some of the foreseeable adverse events related to general anesthesia that can be observed in both the control and investigational group: nausea, vomiting, hypoxemia, hypercapnia, emergence delay, agitation, hypertension, hypotension, postoperative pulmonary infection, intraoperative cardiac arrhythmias, myocardial ischemia, myocardial infarction, cardiac arrest, stroke, pulmonary embolism, intraoperative awareness, hypoventilation, hyperventilation, volutrauma, and barotrauma. The previous events can lead to death.

The following are foreseeable adverse events related to the use of the investigational Et Control option (this excludes surgical procedure related events and drug related events). Although each one of these events could occur through a failure specific to Et Control, these events are not exclusive to Et Control and can also occur with Aisys CS operating in the conventional fresh gas mode as indicated above.

**Table 10-1 – Anticipated Adverse Events and Device Effects**

Event	Machine Failure	General Anesthesia	Aisys CS 	Et Control
Hypoxia	Insufficient oxygen delivery	x	x	x
	Incorrect oxygen concentration of fresh gas flow	x	x	x
	Insufficient ventilation	x	x	x
Hyperoxia	Excessive oxygen delivery	x	x	x
Cardiac Arrest	Incorrect anesthetic agent delivery	x	x	x
Intra-operative Awareness	Insufficient AA delivery	x	x	x
Hypertension	Insufficient anesthetic agent delivery	x	x	x
Hypotension	Excessive anesthetic agent delivery	x	x	x
Airway Fire	Electro-cautery in airway with high O 2	x	x	x

Adverse event assessment will be conducted from the time the subject provided consent to the end of the subject's participation in the study.

There is always a chance of unexpected risks. Throughout the study, the Sponsor will evaluate and update safety information in study documents.

**Study Title:** Multi-site Anesthesia randomized controlled Study of End tidal control (Et Control) compared to conventional anesthesia Results (MASTER-Anesthesia Trial)  
**Study No:** 123.07-2015-GE5-0002

GE Healthcare

